7.6. Dose Selection

Multiple Comparison Procedure Modelling (MCP-Mod) will be used to estimate SM04690 dose response compared to vehicle using the Week 24 baseline-adjusted ANCOVA analysis of the primary and secondary outcome measures in the FAS and all three OA phenotypes described in Section 7.1. MCP-Mod will use both monotonic (e.g. linear) and non-monotonic (e.g. beta-mod, quadratic, emax) models in exploring outcomes’ dose response relationship.

8. SAFETY ANALYSIS

The analysis of safety outcome measures will be performed on the SAS.

8.1. Adverse Events

All adverse events (AEs) collected in this study are TEAEs. AEs will be presented in summary tables depicting the number of AEs and the number and percent of unique subjects experiencing each AE within each treatment group. The following summaries will be provided:

- AEs by seriousness, toxicity grade severity and relationship to study product
- AEs by MedDRA system organ class and preferred term
- AEs by preferred term, sorted by prevalence

Separate subject-level listings will be provided for all serious and non-serious AEs.

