SM04690 was tested in a single phase 1 clinical trial (SM04690-01) in subjects with moderately to severely symptomatic OA of the knee, which was completed on 17Sep2015. The trial was a placebo-controlled, double-blind, dose-escalation study of three concentrations of SM04690 (0.03, 0.07, and 0.23 mg per 2 mL injection), conducted in the US. In each dose cohort, subjects were randomized to active or vehicle at a ratio of 16 active: 4 vehicle. Subject clinic visits occurred on Day 1 and 2, and Weeks 1, 2, 4, 8, 12, and 24. Each successively higher concentration cohort was enrolled after completion of treatment and review of safety data from the previous cohort by a Safety Review Committee. The Safety Review Committee was comprised of the Samumed medical monitor, the site Investigators, and an independent rheumatologist. A total of 33/61 (54.1%) exposed subjects reported no AEs. One SAE (paroxysmal tachycardia) reported was deemed unrelated to study medication by the reporting Investigator. No clinically significant safety concerns or differences among study groups were noted with regard to vital signs, clinical laboratory results, ECGs, or AEs. Based upon these data, a single intra-articular (IA) injection of SM04690 into the knee of OA subjects appeared safe and

well-tolerated.

SM04690 is currently being tested in a phase 2 clinical trial in subjects with moderately to severely symptomatic OA of the knee. The trial is a placebo-controlled, double-blind, parallel group study of three concentrations of SM04690 (0.03, 0.07, and 0.23 mg per 2 mL injection) injected into the target knee joint, conducted in the US. Subjects were randomized at a ratio of 1:1:1:1 (0.03 mg active per 2 mL injection: 0.07 mg active per 2 mL injection: 0.23 mg active per 2 mL injection: placebo). Clinic visits occurred on Treatment Visit Day 1 and Follow-up Weeks 4, 13, 26, 39 and 52 [End of study (EOS)]/Early Termination (ET). As of 30Jun2016, 455 subjects have been randomized. An interim analysis was conducted after all subjects had completed their Week 26 visit. Unblinding in support of the interim analysis occurred on 20Oct2016. As of this date, there has been no obvious dose response or difference from placebo with respect to the most frequently reported AEs, SAEs, or in AEs that led to subject withdrawal.

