7. STUDY PROCEDURES AND SCHEDULE

7.1 STUDY PROCEDURES/EVALUATIONS

7.1.1 STUDY SPECIFIC PROCEDURES

Collection of Adverse Events Data

Data regarding treatment-emergent adverse events (TEAEs) will be collected in this study. TEAEs are events that occur during the course of the study that are not present prior to Day 1 study medication injection, or, if present at the time of study medication injection, have worsened in severity during the course of the study. TEAEs will be assessed at each study visit from the time of study medication injection on study visit Day 1 through Week 24 (EOS)/ET.

Each subject will be observed and queried by the Investigator or the Investigator's designee at each study visit for any continuing TEAEs or new TEAEs since the previous visit. The subject may be asked to return to the site for an unscheduled visit if a TEAE occurs between study visits, and if, in the opinion of the Investigator, the TEAE requires a study visit for full evaluation. Any TEAE reported by the subject or noted by the Investigator or the Investigator's designee will be recorded within the eCRF. The following information will be recorded for each TEAE: description of the event, date of onset and resolution, etiology, and severity as assessed by the Investigator according to the "Guidance for Industry: Toxicity Scale for Healthy Adult and Adolescent Volunteers Enrolled in Preventive Vaccine Trials" ([Appendix 1](#)), causal relationship

to study medication, outcome, and any treatment given.

TEAEs that are not serious and are ongoing at the subject's last visit will be followed until the study close-out visit, if requested. Serious adverse events that are not resolved or stabilized during this time period will be followed until resolution or stabilization.

Medical History

A medical history will be obtained at Screening Visit 1 and Day 1 with a follow-up at Week 24 (EOS)/ET. Medical history at Screening Visit 1 will include demographic data (e.g., age, race, ethnicity) and usage of assistive devices. In addition, medical information will also be recorded, including all (1) medical conditions and disease states that require current or ongoing therapy and (2) other medical conditions and disease states that, in the opinion of the Investigator, are relevant to the subject's study participation. Review of medical history at the Week 24 (EOS)/ET visit will only be to capture End Dates of any ongoing medical history collected at screening.

Physical Examination

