7.3.4 FINAL STUDY VISIT

Week 24 End of Study (EOS)

This final study visit should occur on Day 169 with a window of + 7 days.

The following procedures and assessments will be performed at Week 24 (EOS):

- Collection of TEAE and concomitant procedures/therapies/medication data
- Review of medical history
- Vital signs measurements (pulse, blood pressure, respiration rate, and temperature)
- Physical examination, including knee examination of both knees
- Weight measurement
- Venipuncture and collection of samples for clinical laboratory tests
- Radiograph – bilateral in weight-bearing fixed flexion position, posterior-anterior (PA) view X-ray
- Physician Global Assessment
- Evaluation of success of blinding
- Return of electronic device

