8.3 TIME PERIOD AND FREQUENCY FOR EVENT ASSESSMENT AND FOLLOW-UP

The reporting period for TEAEs starts after the injection of study medication on Day 1 and ends after the final study visit.

TEAEs must be followed until resolution by the Investigator. Resolution is defined as the return to baseline status or stabilization of the condition with the expectation that it will remain chronic. TEAEs that are not serious and are ongoing at the subject's last visit will be followed until the

study close-out visit, if requested. Serious adverse events that are not resolved or stabilized during this time period will be followed until resolution or stabilization.

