8.5. Extent of Exposure

All treated subjects received a single injection. A list of lot numbers used in this study will be provided in the clinical study report.

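### SAP 8.1 tabulates adverse events only over the full 24 weeks after a single injection, so an early excess in a term that is common in knee OA would be hard to see between arms

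*SAP*

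**What the plan says.** Exposure is a single event. SAP 8.5 states: "All treated subjects received a single injection". Collection then runs for the whole study. Protocol 8.3 has: "The reporting period for TEAEs starts after the injection of study medication on Day 1 and ends after the final study visit". Protocol 7.3.4 fixes the end: "This final study visit should occur on Day 169 with a window of + 7 days".

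SAP 8.1 sets no narrower window: "All adverse events (AEs) collected in this study are TEAEs". Its general rule, applied separately to every arm, is that "AEs will be presented in summary tables depicting the number of AEs and the number and percent of unique subjects experiencing each AE". Three summaries follow. The first is "AEs by seriousness, toxicity grade severity and relationship to study product". The second is by system organ class and preferred term. The third is by preferred term in order of frequency. Subject-level listings are added, and their columns are not specified. Protocol 10.4.3 and 10.4.4 ask for incidence, seriousness, severity and relationship, and add nothing on timing.

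The timing data exist. For each event, Protocol 7.1.1 requires "description of the event, date of onset and resolution, etiology, and severity as assessed by the Investigator", among other items.

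**The concern.** Safety and tolerability is the whole secondary objective, and treatment-emergent events are the first secondary endpoint. For a one-off intra-articular injection, one main tolerability question is what happens in the first days or weeks. Protocol 2.3.1 lists pain at the injection site, knee swelling, bleeding, bruising, infection and joint injury as procedure risks. It also reports a phase 1 dose-limiting event of increased knee pain, judged probably related.

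Knee pain and swelling are also things that people with knee OA may report at any time. In the planned tables, knee pain starting on Day 2 and knee pain starting in Week 20 fall in the same cell. With four doses, vehicle and sham, the trial is well placed to separate the early effects of needle, vehicle and drug, but only if a table shows the early period. What is at stake is how visible an early signal is in the summaries. No planned estimate is biased.

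**Working it through.** **The plan's own figure.** 24 × 7 + 1 = 169, so Day 169 is 168 days after Day 1, as Protocol 7.3.4 has it. After a 7-day window, 168 − 7 = 161 days remain, or 161/30.44 = 5.3 months. After a 28-day window, 140 days remain, or 4.6 months. A 7-day window is 7/168 = 4.2% of the counting period.

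**Inputs from the documents.** About 630 subjects in six equal arms (Protocol 10.5): 630/6 = 105 per arm.

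**Assumptions, because the documents give no such rates.**
- Background risk over 24 weeks, b, for one preferred term: 5%, 10% or 15%, at a constant hazard and the same in both arms.
- Extra acute risk, a, in one arm, all within Days 1–7: 3%, 6% or 10%.
- Complete follow-up and exact onset dates.

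**Formulas.** For a table limited to onset in the first w days, the reference arm has q(w) = 1 − (1 − b)^(w/168). The other arm has p(w) = 1 − (1 − q(w))(1 − a). Power is that of a two-sided exact Fisher test at 0.05, 105 against 105.

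**One case in full: b = 10%, a = 6%.**

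| Onset window | Arm with excess | Reference arm | Difference | Ratio | Expected subjects of 105 |
|---|---|---|---|---|---|
| 24 weeks | 15.4% | 10.0% | 5.4 points | 1.5 | 16.2 vs 10.5 |
| Days 1–28 | 7.6% | 1.7% | 5.9 points | 4.4 | 8.0 vs 1.8 |
| Days 1–7 | 6.4% | 0.4% | 6.0 points | 14.6 | 6.7 vs 0.5 |

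The absolute difference hardly shrinks; it falls only by the factor 1 − q(w). What changes is the ratio, and the amount of background noise in which the difference has to be seen.

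**Power for one arm against another, for b = 5% / 10% / 15%.**

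| Acute excess | 24 weeks (planned) | Days 1–28 | Days 1–7 |
|---|---|---|---|
| 3% | 8.3 / 6.3 / 5.4% | 10.7 / 10.3 / 9.6% | 10.1 / 10.4 / 10.6% |
| 6% | 25.3 / 16.2 / 12.2% | 48.5 / 40.3 / 34.7% | 57.2 / 53.8 / 50.7% |
| 10% | 57.3 / 38.4 / 28.6% | 87.2 / 79.5 / 72.2% | 93.5 / 91.2 / 88.9% |

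**A term with little late background: b = 1%, a = 6%.** Power is 46.9% over 24 weeks, 57.9% for Days 1–28 and 60.0% for Days 1–7. The gain is modest.

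**All four doses pooled against vehicle (420 vs 105), a = 6%.** Power is 39.9 / 25.4 / 19.0% over 24 weeks and 78.4 / 65.6 / 55.1% for Days 1–28. This gain is available only if the table has a pooled-active column, which SAP 8.1 does not plan.

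**The case against.** The strongest reply is that nothing planned is wrong. Protocol 10.4.4 plans no formal safety analysis, so every power figure above belongs to a test that nobody will run. The protocol asks for incidence, seriousness, severity and relationship, and SAP 8.1 delivers these. That stands: the figures measure visibility only, and an onset split is an added display.

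Second, timing is partly covered. The relationship categories in Protocol 8.2.2 take timing into account and extend to the injection itself, relationship is tabulated, and every event is listed. This helps, but only in part. Relationship is the investigator's judgement, the SAP does not say that it will be crossed with preferred term, and listings for some 630 subjects do not replace a comparison of arms.

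Third, the size depends on assumed rates. With a 3% excess no window shows the signal for a single dose. Also, the named procedure risks come from the needle or the excipients. Vehicle shares both and sham shares the needle, so that text does not by itself predict an excess of drug over vehicle. Both points stand.

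Fourth, early onset dates are weak. The first visit after injection is Day 29 (+3 days), and the electronic diary does not collect adverse events. Dates within Days 1–7 will rest largely on recall a month later or on spontaneous report, while the calculation treats them as exact. This stands, and it makes Days 1–28 the more reliable window.

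Two stronger readings are tempting. One is that every acute reaction is diluted; the 1% background case shows that this fails for terms with little late background. The other takes a background for any adverse event from phase 1, where "A total of 33/61 (54.1%) exposed subjects reported no AEs", leaving 28/61 = 45.9% with at least one. That is not a clean background. It pools active and vehicle subjects (16:4 per cohort), all of them injected, so acute reactions are already in it, and it comes from a denser early visit schedule (Protocol 2.2).

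**Conclusion.** The omission is real. There is one injection, about 24 weeks of counting, recorded onset dates, and no summary that uses them. Its consequence is limited to terms with appreciable background in this population. For these, at an assumed 24-week background of 5–15%:
- An acute excess of 6% has power 12–25% in the planned tables, 35–49% with onset in Days 1–28 and 51–57% in Days 1–7.
- An excess of 10% has 29–57%, 72–87% and 89–94%.
- An excess of 3% has 5–8% in the planned tables and about 10–11% in either window, so the split scarcely helps a single-dose comparison.

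These ranges rest on a constant background hazard, an excess confined to the first week, 105 per arm and exact onset dates. Imprecise dates would reduce the gain, most of all for Days 1–7. Which terms have high or low late background is a clinical expectation, since the documents give no rates. A reader might infer that the planned safety analysis is biased or falls short of the protocol; the documents support neither. This is a worthwhile, inexpensive addition to the descriptive tables.

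**What to change.** In SAP 8.1, keep the 24-week tables as they are and add one descriptive table by system organ class and preferred term, with rows for any event and any related event:
- **Onset periods:** Days 1–7, cumulative Days 1–28, and after Day 28. The first two boundaries match Week 1 and Weeks 1–4 as SAP 9.3 defines weeks.
- **Columns:** each of the six treatment groups, plus all active doses pooled.
- **Counting rule:** a subject counts once per term in each period in which an event with that term starts. State that the periods overlap or can share subjects, so their counts do not add up to the 24-week total.
- **Footnote:** the first visit after injection is Day 29, early onset dates rest largely on recall or spontaneous report, and Days 1–28 is the more reliable window.

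The cost is SAP wording and a few more tables, from onset dates that the eCRF already holds. No new data, visits or tests are needed, and no planned output is lost.

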8.2. Clinical Laboratory

All chemistry, hematology and urinalysis results from the central lab will be summarized into shift tables as normal, non-clinically significant abnormal, and clinically significant abnormal. Assessments of clinical significance for abnormal values were made by the investigator on results that were outside of the normal range or had a toxicity grade of 1 or greater. Shift tables will compare the number and percent of assessments from each visit to baseline values for each treatment group. Abnormal results for each subject will be provided in listings that will include assay name, result, normal range and an explanation for clinically significant values.

Abnormal urine microscopy and manual differential assessments will be listed for each subject.

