2.3 POTENTIAL RISKS AND BENEFITS

2.3.1 KNOWN POTENTIAL RISKS

Study Medication SM04690

The study drug SM04690 and procedures have risks and discomforts. The study drug SM04690 modulates the Wnt pathway. Potential risks associated with modulation of this pathway include gastrointestinal distress, inhibition of bone formation, and myelosuppression.

SM04690 drug product is a suspension of SM04690 in diluent containing carboxymethylcellulose sodium and polysorbate 80 in phosphate buffered saline. Potential risks associated with carboxymethylcellulose sodium and polysorbate 80 include allergic reaction and hypersensitivity. Serious allergic reactions may be associated with increased risk of death, but serious allergic reactions are rare and, as of 28 June 2017, have not been reported in any subject on human studies testing SM04690. Symptoms of an allergic reaction may include rash, wheezing and difficulty breathing, dizziness and fainting, swelling around the mouth, throat or eyes, a fast pulse, or sweating.

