The results of the clinical laboratory tests will be reported on the laboratory's standard reports. The Investigator must review all laboratory reports in a timely manner, noting "not clinically significant" (NCS) or comment on the clinical significance (clinically significant: yes/no) of any result that is outside the normal range for the laboratory or has a toxicity grade of 1 or greater, then date and initial the report. The Investigator must report all laboratory results that are BOTH outside the normal range for the laboratory or has a toxicity grade of 1 or greater AND, in the opinion of the Investigator, are clinically significant. If any abnormal, clinically significant laboratory measure is found prior to study medication injection, the subject is to be excluded. If it is found after study medication injection, it should be reported as a TEAE.

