10.4.4 SAFETY ANALYSES

Safety analyses will be performed on subjects who receive a study injection. Safety assessments include physical examinations, vital signs, clinical laboratory tests, solicitation of TEAEs and concomitant medications, and general medical evaluations. No formal statistical analyses are planned. Safety will be evaluated based on the incidence, seriousness, severity, and relationship of TEAEs and by changes in clinical laboratory parameters and vital signs, relative to baseline. Changes from baseline in the amount and duration of NSAID usage will be monitored.

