Total Protein – Hypoproteinemia g/dL	5.5 – 6.0	5.0 – 5.4	< 5.0	--
Alkaline phosphate – increase by factor	1.1 – 2.0 x ULN	2.1 – 3.0 x ULN	3.1 – 10 x ULN	> 10 x ULN
Liver Function Tests –ALT, AST increase by factor	1.1 – 2.5 x ULN	2.6 – 5.0 x ULN	5.1 – 10 x ULN	> 10 x ULN
Bilirubin – when accompanied by any increase in Liver Function Test increase by factor	1.1 – 1.25 x ULN	1.26 – 1.5 x ULN	1.51 – 1.75 x ULN	> 1.75 x ULN
Bilirubin – when Liver Function Test is normal; increase by factor	1.1 – 1.5 x ULN	1.6 – 2.0 x ULN	2.0 – 3.0 x ULN	> 3.0 x ULN
Cholesterol	201 – 210	211 – 225	> 226	---
Pancreatic enzymes – amylase, lipase	1.1 – 1.5 x ULN	1.6 – 2.0 x ULN	2.1 – 5.0 x ULN	> 5.0 x ULN

* The laboratory values provided in the tables serve as guidelines and are dependent upon institutional normal parameters. Institutional normal reference ranges should be provided to demonstrate that they are appropriate.

** The clinical signs or symptoms associated with laboratory abnormalities might result in characterization of the laboratory abnormalities as Potentially Life Threatening (Grade 4). For example, a low sodium value that falls within a grade 3 parameter (125-129 mE/L) should be recorded as a grade 4 hyponatremia event if the subject had a new seizure associated with the low sodium value.

*** “ULN” is the upper limit of the normal range.

Hematology *	Mild (Grade 1)	Moderate (Grade 2)	Severe (Grade 3)	Potentially Life Threatening (Grade 4)
Hemoglobin (Female) - gm/dL	11.0 – 12.0	9.5 – 10.9	8.0 – 9.4	< 8.0
Hemoglobin (Female) change from baseline value - gm/dL	Any decrease – 1.5	1.6 – 2.0	2.1 – 5.0	> 5.0
Hemoglobin (Male) - gm/dL	12.5 – 13.5	10.5 – 12.4	8.5 – 10.4	< 8.5
Hemoglobin (Male) change from baseline value – gm/dL	Any decrease – 1.5	1.6 – 2.0	2.1 – 5.0	> 5.0
WBC Increase - cell/mm ³	10,800 – 15,000	15,001 – 20,000	20,001 – 25,000	> 25,000
WBC Decrease - cell/mm ³	2,500 – 3,500	1,500 – 2,499	1,000 – 1,499	< 1,000
Lymphocytes Decrease - cell/mm ³	750 – 1,000	500 – 749	250 – 499	< 250
Neutrophils Decrease - cell/mm ³	1,500 – 2,000	1,000 – 1,499	500 – 999	< 500
Eosinophils - cell/mm ³	650 – 1500	1501 - 5000	> 5000	Hypereosinophilic
Platelets Decreased - cell/mm ³	125,000 – 140,000	100,000 – 124,000	25,000 – 99,000	< 25,000
PT – increase by factor (prothrombin time)	1.0 – 1.10 x ULN**	1.11 – 1.20 x ULN	1.21 – 1.25 x ULN	> 1.25 ULN
PTT – increase by factor (partial thromboplastin time)	1.0 – 1.2 x ULN	1.21 – 1.4 x ULN	1.41 – 1.5 x ULN	> 1.5 x ULN

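### SAP 8.2 gives laboratory values no numeric summary, so falls in blood counts that stay in range and ungraded appear in no planned laboratory table or listing, although myelosuppression is a named risk

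*SAP*

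**What the plan says.** SAP 8.2 covers chemistry, haematology and urinalysis together. Results "will be summarized into shift tables as normal, non-clinically significant abnormal, and clinically significant abnormal". The layout is by visit and arm: "Shift tables will compare the number and percent of assessments from each visit to baseline values for each treatment group". The only other output for these panels is that "Abnormal results for each subject will be provided in listings", with the assay, the value and the normal range.

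The middle and last categories depend on the investigator's opinion of clinical significance, which was given on "results that were outside of the normal range or had a toxicity grade of 1 or greater". SAP 8.2 does not say whether that wider set also defines abnormal for the table.

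Three parts of the protocol bear on this:
- Section 2.3.1: "Potential risks associated with modulation of this pathway include gastrointestinal distress, inhibition of bone formation, and myelosuppression".
- Section 10.4.1 provides n, mean, SD, median, minimum and maximum for continuous variables.
- Section 10.4.4 says safety will be evaluated in part "by changes in clinical laboratory parameters and vital signs, relative to baseline".

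SAP 8.3 gives vital signs those same statistics at baseline, and the change from baseline at each later visit. SAP 8.2 has nothing equivalent.

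**The concern.** Safety and tolerability are the secondary objective, and blood counts are drawn at Screening Visit 1 and Weeks 4, 12 and 24. A pharmacological effect on the marrow would be expected to shift the whole distribution of counts before many subjects cross a limit. A three-category table registers only the crossings. It does not separate low from high, and it does not show size.

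Listings and adverse event tables do not fill the gap. Listings hold abnormal results only. Under Protocol 7.2.1 a laboratory result becomes a TEAE only if it is abnormal and the investigator judges it clinically significant. A fall that stays in range and ungraded meets neither condition. At stake is whether the study report can show, or reassuringly rule out, a dose-related shift in the parameters tied to a risk that the protocol itself names.

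**Working it through.** The plan states no figure for this summary, so there is none to reproduce. The check sets the grading rules against the table, then compares how much signal each display keeps.

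**Inputs from the documents**
- About 630 subjects in six equal arms (Protocol 10.5): 630/6 = 105 per arm.
- Appendix 1, Table A2: Grade 1 neutrophils are 1,500–2,000 cells/mm³ and Grade 1 platelets 125,000–140,000. White cells, neutrophils, lymphocytes and platelets have absolute cut-offs only.
- Haemoglobin also has change rows, for example "Hemoglobin (Female) change from baseline value - gm/dL". For both sexes Grade 1 is any fall up to 1.5 g/dL, and Grade 3 is a fall of 2.1–5.0.

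**Assumptions (not in the documents)**
- Normally distributed values, 2.5% beyond each normal limit, and baseline-to-visit correlation 0.5–0.8.
- Two-sided 0.05, used only as a yardstick.
- Further assumptions are stated where they are used.

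**Step 1: what is not captured.** Neutrophils going from 6,000 to 2,100 fall by 3,900 and carry no neutrophil grade. If the laboratory's lower limit is at or below 2,100, the result is tabulated normal to normal and is not listed.

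**Step 2: abnormal means out of range.** For a true fall of d between-subject SDs:
- Below the lower limit: Φ(−1.96 + d). With d = 0.5 this is Φ(−1.46) = 7.2%, against 2.5%, so about 93% stay at or above the limit.
- Pooled low or high: Φ(−1.96 + d) + 1 − Φ(1.96 + d).
- Power for proportions: Φ[(|p1 − p0| − 1.96·SE0)/SE1], with SE0 from the pooled proportion and SE1 from the separate ones.
- Power for mean change: Φ[d/(√(2(1−r))·√(2/105)) − 1.96].

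| Fall | Pooled abnormal | Power, pooled table | Power, mean change (r = 0.5 to 0.8) |
|---|---|---|---|
| 0.25 SD | 5.0% → 5.7% | 4% | 44% to 82% |
| 0.5 SD | 5.0% → 7.9% | about 13% | 95% to 100% |

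Splitting low from high raises the table's power at 0.5 SD to 36% (2.5% → 7.2%).

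**Step 3: the same in neutrophil units.** Assume mean 4.2, SD 1.5 (×10⁹/L) and a true fall of 0.5, with the Grade 1 line at 2.0 as the cut-off.
- Share below the line: Φ((2.0 − 4.2)/1.5) = 7.1%, rising to Φ((2.0 − 3.7)/1.5) = 12.9%.
- z = 0.0573/√(0.071×0.929/105 + 0.129×0.871/105) = 1.39.
- Baseline-adjusted change: z = 0.5/(1.5·√(1−ρ²)·√(2/105)) = 2.79 at ρ = 0.5 and 3.38 at ρ = 0.7.

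**Step 4: abnormal also includes grade 1 or greater.** For white cells, neutrophils and platelets this adds only an absolute cut-off, so Step 1 still applies. For haemoglobin, any fall counts:
- With no drug effect, within-subject SD 0.4–0.8 g/dL and rounding to 0.1, simulation puts 46–48% of each arm in the abnormal category at a given visit. At one or more of three visits the share is about 72–73% (1 − 1/4 = 75% if there were no ties).
- Suppose 10% of treated subjects have a large drop and the rest behave as under no effect. Taking 50% as the chance rate, abnormal becomes 0.5×0.9 + 0.1 = 55%, against 50% (power 11%). In a grade table with an assumed 1% background it is 0.01×0.9 + 0.1 = 10.9%, against 1% (power 86%).
- A uniform fall of 0.5 between-subject SD moves any decrease from 50% to 69–79% (power 81–99%). That would be seen, but not its size.

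**The case against.** **The shift table meets the protocol.** A baseline-to-visit shift is literally a change relative to baseline, and the Protocol Summary speaks of clinically significant laboratory changes. This stands as far as it goes: SAP 8.2 does not contradict Protocol 10.4.4. It does not answer 10.4.1, and 10.4.4 treats laboratory values and vital signs alike while the SAP does not.

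**Graded results are seen elsewhere.** If grade 1 or greater counts as abnormal, a large haemoglobin fall is rated and listed with its value. If judged clinically significant, it is also a TEAE, tabulated by toxicity grade under SAP 8.1. That is true, but it depends on investigators at about 80 sites and does not reach ungraded falls.

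**Prior data are reassuring.** Treatment is a single injection, and phase 1, with doses up to 0.23 mg, reported no clinically significant laboratory concern. That lowers the prior worry. Phase 1 had 61 exposed subjects and no 0.15 mg arm.

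**Stronger readings that the documents do not support**
- A reader might infer that any fall in blood counts is hidden however abnormal is read. Step 4 shows that a uniform haemoglobin fall would appear under the wider reading.
- A man going from 16.5 to 13.6 g/dL has fallen 2.9 g/dL, which is Grade 3 by change, yet sits just above the Grade 1 absolute band of 12.5–13.5. A reader might assume he is tabulated normal to normal under the narrow reading. That depends on the laboratory's lower limit, which the documents do not give.
- A reader might suppose that laboratory data feed dose selection. SAP 7.6 rests on MCP-Mod of efficacy outcomes.
- The baseline clinically significant row should be empty, because "If any abnormal, clinically significant laboratory measure is found prior to study medication injection, the subject is to be excluded". That is not a defect and loses nothing that emerges on treatment.

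**Conclusion.** The point holds as a gap in SAP 8.2. The section plans no numeric summary of laboratory values, pools highs and lows, and leaves abnormal undefined. Falls in neutrophils, white cells or platelets that stay in range and above the Appendix 1 cut-offs therefore reach no planned laboratory summary or listing. Under the wider reading of abnormal, the haemoglobin category is filled by chance in nearly half of each arm at each visit. The size of a fall, or a large fall in a minority, is then lost unless an investigator calls it clinically significant.

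The loss is large under plausible inputs, but the z and power figures are illustrative. The SDs, correlations, normality and share beyond the limits are assumed, and Protocol 10.4.4 plans no formal safety test. The textual gap needs none of those assumptions. This should be changed; it does not threaten the efficacy analysis.

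**What to change.** In SAP 8.2, keep the shift table and:
1. **Essential:** for each continuous laboratory analyte, report n, mean, SD, median, minimum and maximum of the value and of the change from baseline, by treatment group and visit (Weeks 4, 12 and 24), as SAP 8.3 does for vital signs.
2. State whether abnormal means out of range only or also toxicity grade 1 or greater, and split low from high.
3. **Supplement:** add a shift table from baseline to worst post-baseline Appendix 1 grade by treatment group, with haemoglobin graded by absolute value and by change shown separately. This does not replace item 1. Neutrophils going from 6,000 to 2,100 stay at grade 0, and alkaline phosphatase is graded only for increases.

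The cost is SAP wording and a few extra tables from central laboratory data already collected. No new sample, visit or staff is needed.
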